3.12.2 Lost to follow up

If a subject fails to attend the clinic for a required study visit, the site should attempt to contact the subject and re-schedule the missed visit as soon as possible. The site should also counsel the subject on the importance of maintaining the assigned visit schedule and confirm whether or not the subject wishes to and/or should continue in the study based on previous noncompliance. In cases where the subject does not return for the rescheduled visit or cannot be reached to reschedule the missed visit, the site should make every effort to regain contact with the subject (3 telephone calls and if necessary, a certified letter to the subject's last known mailing address) so that they can appropriately be withdrawn from the study. These contact attempts should be documented in the subject's medical record. If the subject continues to be unreachable, only then will he/she be considered to have withdrawn from the study with a primary reason of "Lost to Follow-up". For all other subjects withdrawing from the study, an alternative reason for discontinuation should be recorded in the eCRF. Every effort should be made to collect survival status (whether the subject is still alive).

3.12.3 Reason for study withdrawal

The primary reason for study withdrawal will be recorded in the eCRF. When a subject withdraws consent, the Investigator should document the reason if known to the investigator team (if reason specified by the subject) in the eCRF.

The primary reason for study withdrawal will be categorised as:

- Adverse event as decided clinically by the PI team or after discussion with the CI.
- Study closed/terminated
- Lost to follow-up
- Pregnancy
- Withdrew consent
 - subject relocated
 - frequency of visits
 - burden of procedures
 - adverse event
 - other (specify)

3.12.4 Follow-up contact

A safety follow-up contact will be made 7 days (-1/+4) following the completion of the randomised treatment period at 12 months or following the Final Assessment Visit (whichever comes first).

The follow-up contact can be made by phone call or by site visit. The following procedures will be performed:

- Adverse event assessment
- Concurrent medication assessment
- COPD exacerbation assessment

Subjects who have successfully completed all on-treatment randomised visits will be discharged from the study upon completion of the safety follow-up contact.

4. INVESTIGATIONAL MEDICINAL PRODUCT AND PLACEBO

4.1 STUDY DRUG

4.1.1 Study Drug Identification

Pre randomisation Washout Phase for all patients – 4 weeks	
ANORO ELLIPTA inhaler: 55/22 (combination of umeclidinium 55mcg and vilanterol 22mcg) one puff once a day.	

Post randomisation IMP Treatment Phase – 12 months		
Arm 1	Arm 2	
ANORO ELLIPTA inhaler: 55/22 (combination of umeclidinium 55mcg and vilanterol 22mcg) one puff once a day	TRELEGY ELLIPTA inhaler: 92/55/22 (combination of umeclidinium 55mcg vilanterol 22mcg and fluticasone furoate 92mcg) one puff once a day.	

Both treatments will be delivered by ELLIPTA™ dry powder inhaler (DPI). The inhaler is not under investigation and will be used according to its indication. Each DPI will contain 30 doses of IMP. Subjects will be instructed to administer medication once daily in the morning for the duration of the treatment period. Subjects will self-administer their first dose of IMP the day after their randomisation visit. On the morning of each subsequent clinic study visit, subjects will be instructed to refrain from taking their morning dose of IMP until instructed to do so by clinic personnel. Subjects will take their last dose of IMP in the clinic during the 12-month visit (or Final Assessment Visit). A safety follow-up will be conducted either by phone call or clinic visit 7 days (-1/+4) after successfully completing that.

4.1.2 Study Drug Manufacturer

Glaxo Smithkline plc

4.1.3 Marketing Authorisation Holder

Glaxo SmithKline plc [name] United Kingdom.

MA Numbers:

Trelegy Ellipta: PLGB 19494/0287 Anoro Ellipta: PLGB 19494/0268

4.1.4 Labelling and Packaging

The IMP will be provided by GSK and sent to the Investigational Supplies Group (ISG) in Edinburgh.

Receipt, over labelling, packaging, QP, storage of supplies and despatch (via courier) to the clinical sites will be carried out by the Investigational Supplies Group (ISG) supported by Edinburgh University, in conjunction with the Lothian Hospital Pharmacy Services.

Two shipments of IMP are planned for each site or as required. The initial shipment will be dispatched following QA check via an approved courier to each site by ISF triggered on receipt of a dispatch request from the Trial coordinating Centre.

This will be followed by a triggered resupply request from the Trial Co-ordinating Centre to ISG and resupply to sites 6 months post activation or as required

4.1.4.1 Preparation and Labelling of IMP

Over labelling is required. Prior to dispensing the study medication, the core text of the label will include:

□Sponsor name, address and telephone number
$\hfill\Box Pharmaceutical dosage form, route of administration, quantity of dose, units, product name and strength$
□Name of Investigator
□ Directions for use
□"For clinical trial use only" or similar wording
□Storage conditions
□Period of use (MM/YYYY format)
□"Keep out of reach and sight of children"

Medication labels will be in the local language and comply with the legal requirements of Annex 13 of the European Union's Good Manufacturing Practice (GMP). They will include storage conditions for the drug, but no information about the patient.

4.1.5 Storage of Study Drug

Study medication will be stored at each Site Pharmacy Study medications will be stored securely, at a temperature not to exceed 30°C, away from direct sunlight and monitored and recorded daily. Once dispensed patients will be advised to store their inhalers in accordance with the storage instructions in the participant information leaflet. Regulatory Release to Site and despatch

Following, receipt, relabelling and being QP certified by ISG, and the Sponsor will provide permission to release the IMP to the study. Shipment of IMP to sites will not take place until approval for release has been received.

First shipment requests will be sent following, confirmation that all regulatory requirements have been met and all start-up procedures have been completed. Sites will be activated once the drug has been receipted and the Sponsor given the green light.

ISG will arrange the despatches to sites in accordance with the agreed ISG SOP.

4.1.6 Management and Accountability of IMP at site

Study medication must be confirmed as received at site prior to patients being recruited.

Pharmacy staff will be responsible for dispensing. All study clinical supplies are to be dispensed on receipt of a signed trial specific prescription.

Pharmacy staff will maintain an accurate record of the receipt and dispensing of the IMP in a drug accountability log.

Patients will be asked to return all unused and used inhalers and packaging at:

- End of 4-week washout
- 6-month follow-up visit
- 12-month follow-up visit or at the time of discontinuation of treatment.

On return of the medicines, the Pharmacy staff will perform a check of returns and this will be recorded on the drug accountability log, according to the pharmacy manual. Compliance information will available to the study team. Unused treatment will be disposed of by the Pharmacy as per local SOP following Sponsor Authorisation.

4.1.7 Prescribing and Dispensing of IMP

Washout: Following screening and eligibility checks a trial specific prescription for the washout medication will be generated, printed and signed by the PI or delegated sub-investigator prior to being sent to Site pharmacy for dispensing.

Post Randomisation: Following randomisation, a trial specific prescription for the allocated study medication will be generated, printed and signed by the PI or sub-investigator prior to being sent to Site pharmacy. The database will generate a randomisation email indicating the randomisation allocation, this will be printed and attached to the signed study specific prescription. To allow for contingency in visit schedule, the site pharmacist will dispense the first 7 months supply (seven inhalers).

6-month follow-up: At the 6-month follow-up visit an additional 6 months' supply will be prescribed and dispensed. A resupply will be manually triggered by pharmacy when residual stock reaches 30% (minimum) and/or as necessary.

Resupply: In the event a resupply is needed (e.g., lost inhaler) to complete the study treatment period, a resupply of the patient's allocated treatment can be requested on provision of an additional prescription.

4.1.8 Destruction of Trial Drug

Any used or unused inhalers returned will be documented in the drug accountability log and destroyed locally in accordance with local policy following Sponsor authorisation.

Any IMP destroyed will be recorded on the Certificate of Destruction and retained within the pharmacy file). A copy of the Certificate of destruction will be sent to the co-ordinating centre.

4.2 DOSING REGIME

Inhalers for both arms will be prescribed once a day for 12 months of the study period.

Arm 1: ANORO ELLIPTA inhaler: 55/22 (combination of umeclidinium 55mcg and vilanterol 22mcg) one puff once a day

Arm 2: TRELEGY ELLIPTA inhaler: 92/55/22 (combination of umeclidinium 55mcg vilanterol 22mcg and fluticasone furoate 92mcg) one puff once a day.

4.3 DOSE CHANGES

No changes to dosage or regimen should be made during the course of the study.

4.4 PARTICIPANT COMPLIANCE

Study drug compliance will be assessed and recorded by trial personnel at the randomisation, six month and twelve-month (end of study) visits. The Investigator or delegate will collect used and unused medication and packaging from the patient.

Study drug compliance will be assessed by checking the dose indicator on the inhalers. Adherence to COPD treatment in this patient population overall is good. However, if a patient failed to meet a minimum 50% compliance with study medication during the washout period (i.e., they did not take the medication for at least 14/28 days with no exceptional circumstances to justify this), they will not be eligible to continue to be randomised. A 50% threshold for compliance will apply for compliance for the duration of the study.

4.5 OVERDOSE

Vilanterol: An overdose would likely lead to effects that are typical for $\beta 2$ adrenoceptor agonists: tremor, headache, and palpitations. Supportive and symptomatic treatment may be indicated.

Fluticasone: Acute inhalation of doses in excess of those recommended may lead to temporary suppression of adrenal function. This does not need emergency action as adrenal function is recovered in a few days.

Umeclidinium: Acute over dosage is not expected to be a clinical problem. Warning would however be issued around usual side effects like visual disturbances, dry mouth, constipation, micturition difficulties and tachycardia. Treatment is usually observation and symptomatic management.

Other side effects to watch out for: of study drugs are likely to be minor and expected. Candidiasis is the main side effect and withdrawal from study treatment will occur if it is marked as persistent and does not respond to symptomatic treatment. Patients should receive treatment with Nystatin 100,000 units four times daily for up to 7 days if candidiasis requires symptomatic treatment. Requirement for another or additional treatment should lead to study withdrawal as alternative treatments may impact the primary outcome.

Paroxysmal bronchospasm is a rare side effect (≥1/10 000 to <1/1000) any patients experiencing this would be withdrawn from treatment, the patient will be assessed, and an alternative therapy instituted, if necessary.

If patients withdraw from the study at some during the trial and do not wish to return for study visits, contact with them will be maintained by the PI, trial manager, research nurse or research assistant to ensure resolution of adverse event(s) and their GP notified. If withdrawal is due to an AE, it will be logged as such on the Adverse Event Log.

The following table summarises the strategy to mitigate some possible side effects from the proposed IMPs.

Potential Risk of Clinical Significance		Mitigation Strategy
Pneumonia in patients with COPD Systemic effects of corticosteroids: bone disorders,	Pneumonia is a class concern for any ICS-containing product for the treatment of COPD. In two replicate 12-month studies, in the FF/VI clinical program, in a total of 3,255 patients with COPD who had experienced a COPD exacerbation in the previous year, there was a higher incidence of pneumonia (6%-7%) reported in patients receiving the FF (at strengths of 50, 100, and 200 µg)/VI 25 µg combination than in those receiving VI 25 µg alone (3%). In some instances, these pneumonia events were fatal (including one fatality on FF/VI 100/25 µg dose). Risk factors for pneumonia observed in these studies included current smokers, patients with a history of prior pneumonia, patients with a body mass index <25 kg/m2 and patients with an FEV1<50% predicted. These factors should be taken into consideration when using an ICS in patients with COPD with coexistent bronchiectasis. Pneumonia risk will be important in the benefit-risk assessment for FF/UMEC/VI in COPD patients, hence a robust risk mitigation strategy is being proposed. A decrease in bone mineral density and the risk of fractures is a class	 the protocol (section 3.5) Collection of information on previous history of pneumonia in past 12 months, including hospitalisation at baseline Use of pneumonia electronic Case Report Form (eCRF) All diagnoses of pneumonia (radiographically confirmed or unconfirmed) must be reported as an AE or SAE (if applicable) CXR read required whenever a patient has suspected pneumonia
bone mineral density decrease and associated fractures	and the risk of fractures is a class concern for any ICS-containing product for the treatment of COPD. This is however a very small risk as has been shown in previous studies.	bone systemic corticosteroid effects will be conducted through assessment of reported bone adverse events (Review AE/SAE reports)

Systemic effects of corticosteroids: Cortisol suppression	Although all steroids are likely to have some impact on the hypothalamic pituitary axis (HPA axis), the proposed dose of inhaled FF in this study is unlikely to lead to any clinically significant changes. No studies have shown a clinically relevant effect of FF/VI on HPA axis. This includes a formal HPA study in asthma subjects, which assessed the effects of FF/VI 100/25 and 200/25 doses on serum cortisol and 24 hours urinary cortisol excretion, and multiple studies with COPD subjects which monitored 24-hour urinary cortisol. During clinical development of FF & FF/VI, no events of Adrenal Suppression was reported.	
Systemic ocular effects of corticosteroids: glaucoma, cataract, raised intra-ocular pressure	Systemic ocular effects (e.g., cataract and glaucoma) may occur with any inhaled corticosteroid, particularly at high doses prescribed for long periods. However, these effects are much less likely to occur with inhaled corticosteroids compared with oral corticosteroids. During studies with FF and FF/VI in asthma subjects, and with FF/VI and UMEC/VI in COPD subjects, no associated effect on ocular disorders was observed. In addition, no effects on lens opacification were observed on formal ophthalmic assessments in a study with FF/VI, FF and FP in subjects with asthma.	Patients with known narrowangle glaucoma that, in the opinion of the Investigator contraindicates study participation or use of an inhaled anticholinergic, will be excluded from participating in this study. Review AE/SAE reports

Cardiovascular effects of UMEC and VI

UMEC

Cardiovascular effects are a potential class effect associated with antimuscarinic therapies. In the UMEC/VI clinical development program in COPD patients, UMEC/VI was generally well tolerated. Overall, a low number of atrial arrhythmias were reported based on 12-lead ECGs, Holter ECGs, or AEs, of which some occurred with a higher incidence in active treatment groups compared to placebo.

There was no additive effect with the combination over individual components. Few of these findings were reported as SAEs and none were fatal. In a narrow* Major Adverse Cardiac Event (MACE) analysis, the incidence of non-fatal myocardial infarction (MedDRA PTs of myocardial infarction and acute myocardial infarction) was low (<1%) across all treatment groups, although small imbalances in exposure

UMEC- and VI containing treatment groups when compared with placebo and tiotropium. There was no obvious dose relationship or additive effect from the combination. Whether this represents a true effect is difficult to determine due to the small numbers.

adjusted frequency were observed

During clinical studies in COPD (62.5 and 125 µg daily dose of UMEC) and in Healthy Volunteers (in the Thorough QT study, UMEC 500 µg daily dose), no effect was observed on heart rate, blood pressure or QT.

VI

between

In the FF/VI clinical development program in patients with COPD, the cardiovascular safety profile of VI and FF/VI was broadly consistent with the known pharmacology of LABAs in patients with COPD. VI at doses up to 100 µg in healthy subjects and subjects with asthma or COPD was not consistently associated with clinically relevant or statistically significant effects on blood pressure after either single or repeat dose administration.

Data from Thorough QT (TQT) studies with FF, FF/VI and UMEC/VI suggest that, at the doses to be used in phase III studies, the closed triple (FF/UMEC/VI) is unlikely to cause clinically relevant effects on QTc. No difference in QTcF was observed between UMEC/VI 125/25mcg or UMEC 500mcg and placebo. UMEC/VI 500/100mcg increased QTcF on average by 8.2msec (90% CI: 6.2, 10.2) at 30 min only. A lack of effect was demonstrated for QTcF with FF/VI 200/25 mcg (for 7 days). At a supratherapeutic dose of FF/VI (800/100 mcg for 7 days), the largest mean time-matched difference from placebo was 9.6 msec (90% CI: 7.2, 12.0) at 30 min only.

- Exclusion criteria as specified in the protocol (section 3.5).
- Collection of cardiovascular risk factors and medical history at baseline
 - ECGs as per protocol
 - Vital sign

 assessments (heart rate and blood pressure) as per protocol
- Review AE/SAE reports

Anticholinergic effects (including constipation, nausea, dry mouth, dysgeusia, glaucoma, raised intraocular pressure and blurred vision, urinary retention, eye pain)	In clinical studies in COPD, few anticholinergic effects were associated with UMEC; those observed included dry mouth, constipation and cough. ICS has a similar class risk of glaucoma and elevated IOP; however, these effects occur by a different mechanism that is not expected to be synergistic or additive when FF is used in combination with UMEC.	Patients with known significant narrow-angle glaucoma, prostatic hyperplasia or bladder outflow obstruction that in the opinion of the Investigator contraindicates study participation will be excluded from participating in the study (see exclusion criterion in section 3.5). Review AE/SAE reports
Hypersensitivity	Although not associated with FF/VI during the clinical studies, isolated cases of hypersensitivity reactions have been observed, post marketing, with the licensed intranasal spray, AVAMYS. In addition, the FF inhaled formulation has had some reports of hypersensitivity-type reactions. FF/VI formulation contains lactose. There have been reports of serious allergic reactions in patients with severe milk protein allergy after inhalation of other powder products containing lactose.	As per exclusion criterion in section 3.5 Review AE/SAE reports

Radiation risk: we envisage no extra radiation risk to these patients (other than performing chest x-rays as part of clinical care for suspected pneumonias). CT scans would have happened prior to enrolment to this study as a part of their usual pathway of clinical delivery pathways.

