3.12 WITHDRAWAL OF STUDY PARTICIPANTS

3.12.1 Study Withdrawal

Participants are free to withdraw from the study at any point or a participant can be withdrawn by the Investigator. If withdrawal occurs, the primary reason for withdrawal will be documented

in the participant's eCRF, if specified by the patient. The participant will have the option of withdrawal from:

- (i) study medication with continued study procedures and collection of clinical and safety data. The final Assessment Visit should be brought forward and they will receive the final follow-up contact.
- (ii) all aspects of the trial but continued use of data collected up to that point. To safeguard rights, the minimum personally-identifiable information possible will be collected. Any patient who withdraws from all aspects of the study will be invited to return to the clinic to have a Final Assessment Visit.

Data will be kept on the CRF/database.

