5.3 STUDY ASSESSMENTS

Investigations (A	All Patients)	Screening and Consenting Visit	Medication Washout Period 4 weeks	Baseline/Randomisation	Telephone Follow-up contact	Month 6 +/- 2 Weeks	Month 12 or Final Assessment +/- 3 Weeks			Exacerbation Visit (Face to face or telephone visits)
Visit Number		Visit 1		Visit 2	Visit 3	Visit 4	Visit 5	Visit 6 *	Visit 7	As necessary
Time relative to	randomisation	- 4w	-4w	0	1m + 2d	6m	12m	1 to 12m	12m + 7d	1 to 12
Time window fo	or evaluation	N/A	N/A	4 weeks ±2 days from screening		+ 2 weeks from randomisation	+ 3 weeks	+2d	+3d	-
Written Informe		✓								
LMP, Pregnancy review (where a	Test & Contraception applicable)	✓		√		✓	✓		✓	
Physical Examin and weight)	ation (including height	✓								✓
Current COPD M	ledications?	✓		✓	✓	✓	✓	✓	✓	✓
Concomitant Me	edications	✓								
Past Medical His	story?	✓								
Demographics		✓								
Stratification				✓						
Lifestyle		✓								
Eligibility review		✓		✓						
Reaffirm Conser				✓		✓	✓		✓	✓
Medication Was	hout & Accountability			✓						
Randomisation				✓						
Spontaneous Sputum	Sputum Colour			✓		✓	✓		✓	
Sputum	Qualitative and Quantitative Microbiology 16S RNA Pyrosequencing			√		√	✓			
Sputum inflammatory assays	Myeloperoxidase (MPO) Free elastase activity			✓		· ·	✓		- v	

Routine Bloods	FBC including								
tests	eosinophil count,				✓	√		1	
	CRP, ICAM-1		ľ		•	•		•	
	U&E's, LFT's								
	Fibrinogen								
Spirometry	FEV1 + FVC;								
	FEV1/FVC; mid	✓	✓		✓	✓		✓	
	expiratory flows								
	(FEF25-75)								
Questionnaires	COPD Assessment								
	Tool		 		✓	✓		✓	✓
	St George's		·		·				
	Respiratory SGRQ-C								
	eathlessness score	✓	✓		✓	✓		✓	
12 Lead ECG		✓			✓	✓		✓	
Vital signs (Pulse, respiratory rate,									
blood pressure, oxygen saturations on		✓	✓		✓	✓		✓	✓
room air and body temperature)									
Exacerbations (Number of and time to			✓	✓	✓	,	✓	√	
1st moderate/sev	vere exacerbation)		V		v	✓		•	
Collection of all AE and SAE data (as in			,	✓	,	,	✓	,	,
section 11)	section 11)		✓		✓	✓		✓	✓
Dispense randomised study			✓		✓				
Medication?									
Study Medication	Study Medication Adherence (&			✓	✓	✓		✓	✓
Accountability check if face to face)									
	,					✓			
						,			
						✓			
								✓	✓

Table 1 of assessments

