6.4 Visit 5 – 12 months/Final Assessment

A final Assessment Visit will be completed for all participants at completion of the study or earlier if required.

The following assessments are expected to be conducted in clinic and must be recorded in the CRF:

- Adverse Events
- Any exacerbations of COPD
- Any changes in concomitant medications
- Pregnancy and contraceptive review (if there is concern of pregnancy, another pregnancy test will be administered)
- Vital signs
- Blood analysis (Biochemistry)
- Sputum collection
- ECG
- ICAM-1 collection
- Adherence to study treatment
- Spirometry
- SGRQ-C assessments
- COPD Assessment Tool (CAT)
- Modified MRC breathless score

- Return of unused study medication and accountability
- Study medication adherence and accountability

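### Protocol 3.12.1(i) brings the final visit forward for anyone who stops study medication, so the 12-month sputum can be lost or mistimed; the candidiasis rule in 4.5 adds to this

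*Protocol*

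**What the plan says.** **Stopping study medication.** Protocol 3.12.1 offers two forms of withdrawal under one heading. Option (i) is withdrawal from "study medication with continued study procedures and collection of clinical and safety data". The sentence that follows says: "The final Assessment Visit should be brought forward and they will receive the final follow-up contact". Option (ii) is withdrawal from all aspects of the trial: "Any patient who withdraws from all aspects of the study will be invited to return to the clinic to have a Final Assessment Visit". Neither option says that a month-12 sputum is still taken.

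**How the early visit is recorded.** Section 6.4, headed as Visit 5, says: "A final Assessment Visit will be completed for all participants at completion of the study or earlier if required". Sputum is collected at that visit. Table 1 gives it a single column, "Month 12 or Final Assessment +/- 3 Weeks".

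**The candidiasis rule.** Section 4.5 says of candidiasis that "withdrawal from study treatment will occur if it is marked as persistent and does not respond to symptomatic treatment". After allowing up to 7 days of nystatin it continues: "Requirement for another or additional treatment should lead to study withdrawal as alternative treatments may impact the primary outcome". Two paragraphs later it makes provision for a subset, "If patients withdraw from the study at some during the trial and do not wish to return for study visits", which implies that others who withdraw do return.

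**Other medications.** Sections 4.7.2 and 4.7.3 keep participants in the study after short antibiotic courses or after starting a restricted drug; under 4.7.3 they may also stay on study drug. Section 4.7.4 prohibits itraconazole and ketoconazole on airway-microbiome grounds, but does not say that a participant who takes them leaves the study.

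**Analysis.** SAP 4.4 defines the primary outcome as log CFU/ml at 12 months minus log CFU/ml at baseline, compared by a two-sample t-test. SAP 3.1 analyses by assigned group whatever treatment was received. SAP 3.4 plans no imputation and makes a sensitivity analysis optional. The SAP has early-exit rules for compliance (4.2) and for censoring in the mortality analysis (4.5.9), but none for the primary outcome.

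**The concern.** An as-randomised comparison at 12 months needs a 12-month value from as many randomised participants as possible, including those who have stopped drug. Option (i) retains these participants in name but moves their last planned sampling visit to the time they stop. Their sputum then carries the Visit 5 label without being a month-12 sample. Depending on how the data are handled, the participant either drops out of the primary analysis or enters it with a shorter exposure.

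Either outcome is decided by something that happened after randomisation. If stopping is related to treatment and to bacterial load, the comparison is no longer fully protected by randomisation. The 10% dropout allowance replaces numbers; it does not correct selection.

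Section 4.5 makes this slightly worse, because it directs an exit whose only stated reason is the primary outcome. That sits awkwardly in a trial with a bacterial culture endpoint that retains participants who take antibiotics. Where a concomitant drug may affect the outcome, recording it and keeping the measurement loses less than removing the participant.

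**Working it through.** **1. The plan's own figure.** Inputs from Protocol 8.1: difference 0.76 log, SD 0.98 log, two-sided 5%, 90% power, 36 per group, 10% dropout. The noncentral-t power of the two-sample t-test at 36 v 36 is 90.06%, so 36 is reproduced. Allowing for dropout, 36 / 0.9 = 40 per group, 80 in total. The allowance is 4 per arm.

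**2. What follows from the text when a participant stops study drug at month t < 12.**

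| Route | What the protocol directs | Month-12 sputum |
|---|---|---|
| 3.12.1(i), drug only | Procedures continue, but the final visit is brought forward | Not provided for; an early sample is recorded as Visit 5 |
| 3.12.1(ii), all aspects | Invitation to a final visit | None; an early sample if the invitation is accepted |
| 4.5, candidiasis beyond nystatin | Study withdrawal, route not named | As (i) or (ii) |

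SAP 4.4 does not say what to do with an early Visit 5 sample.

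**3. Illustrative size.** The documents give no rate of drug discontinuation or candidiasis. *Assumption:* m = 1 to 4 of 36 evaluable participants are affected, all in the triple arm.

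(a) *Early sample not used.* If the cases fall within the 4 per arm already allowed, power stays at 90.1%. If they come on top of that allowance:

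| Triple v dual | Power for 0.76 |
|---|---|
| 35 v 36 | 89.6% |
| 34 v 36 | 89.2% |
| 32 v 36 | 88.2% |

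(b) *Early sample used as the 12-month value.* Further assumption: the effect builds linearly over 12 months. Understatement = (m/36) × (1 − t/12) × 0.76.
- m = 1, t = 9: (1/36) × 0.25 × 0.76 = 0.005 log (0.7%)
- m = 2, t = 6: (2/36) × 0.50 × 0.76 = 0.021 log (2.8%)
- m = 4, t = 3: (4/36) × 0.75 × 0.76 = 0.063 log (8.3%); power at 36 v 36 is then about 84.5%

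(c) *Under the fix, with the 12-month sample taken off drug.* If the effect persists, power is 90.1%. If it has fully reversed, the loss is (m/36) × 0.76:
- m = 1: 0.021 log, power 88.4%
- m = 2: 0.042 log, power 86.5%
- m = 4: 0.084 log (11.1%), power 82.2%

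(d) *Selective loss.* If a share f of one arm is removed and its mean change differs by D from the rest of that arm, the arm mean shifts by f × D. For 4 of 40 (f = 0.10) and an assumed D of 0.5 to 2.0 log, the shift is 0.05 to 0.20 log. Nothing in the documents says what D is, or that it differs from zero.

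**The case against.** **The rule in 4.5 has a rationale.** Section 4.7.4 prohibits two antifungals, itraconazole and ketoconazole, because they might alter the airway microbiome, so 4.5 applies a concern that the protocol holds elsewhere. This stands and narrows the inconsistency with 4.7.2 and 4.7.3. It does not justify an exit from the study, because 4.7.4 attaches none to use of those drugs. It does mean that a change to 4.5 has to be reconciled with 4.7.4.

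**Section 4.5 can be read as drug-only withdrawal.** A reader might infer that 4.5 contradicts itself, since it speaks of withdrawal from treatment and then of withdrawal from the study. The documents support only ambiguity: 3.12.1 uses its study-withdrawal heading for both routes. Even on the milder reading, route (i) still brings the final visit forward.

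**SAP 4.4 already says 12 months.** A reader might infer that a month-3 sample would be analysed as the 12-month value. The SAP does not say so, and its formula, with the Table 1 window, points the other way. Scenario (b) is therefore the less likely handling, and a sentence on it is mostly clarification.

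**The fix can cost more power than the problem.** With 4 cases, dropping the early sample gives 88.2%; keeping an off-drug sample after full reversal gives 82.2%. This stands. What is gained is the as-randomised comparison that SAP 3.1 already chose, not power.

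**The harm is not demonstrated, and the change may come late.** Both are fair. SAP v2.1 is dated June 2025 and describes some scoring as already done.

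**Conclusion.** The point holds as a cheap improvement. Its centre is 3.12.1(i), which covers every stop of study drug; the candidiasis sentence in 4.5 is one contributor. As written, the protocol can lose or mistime the 12-month CFU that SAP 3.1 and 4.4 rely on.

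The effect is unknown and probably small. Under the assumed 1 to 4 losses in one arm beyond the allowance, power is 89.6% to 88.2% against 90.1%; within the allowance there is no loss of planned power. The figures for mistimed samples, selective loss and off-drug dilution rest on assumed counts, timing and effect patterns.

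A reader might infer that the candidiasis rule biases the trial, because candidiasis is called the main side effect and only one arm contains a corticosteroid. An imbalance is plausible on that ground, but the documents give no candidiasis rate, no difference between arms and no link between candidiasis and CFU. Neither a direction nor a size of bias can be claimed.

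**What to change.** 1. **Protocol 3.12.1(i).** State that participants who stop study drug without withdrawing consent keep the scheduled 6- and 12-month visits and sputum, that the final visit is not brought forward, and that the 12-month value enters the as-randomised primary analysis.
2. **Protocol 4.5.** Replace study withdrawal with withdrawal from study treatment under 3.12.1(i), and record the antifungal. Cross-refer to 4.7.4, so that a participant who needs itraconazole or ketoconazole stops study drug but stays in follow-up.
3. **SAP 4.4, before database lock.** As a clarification, state that a Visit 5 sputum outside month 12 ± 3 weeks is described but not used as the 12-month value.

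**Cost.** A sentence or so in each place, plus the cross-reference to 4.7.4. Items 1 and 2 need a protocol amendment, which under Protocol 12.1 goes to the ethics committee, the regulator and local R&D before implementation. No visit is added to the schedule, but participants who stop drug attend the remaining visits instead of one early one. Some 12-month samples will be off drug and can dilute the difference, down to 82.2% power in the worst case shown. If follow-up is nearly complete, items 1 and 2 help few participants and item 3 is the part still usable.
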